e) Flow-chart

Assessment Title	Pre-anesthesia	Anesthesia procedure during surgery	15 minutes PQRS Test	40 minutes PQRS test	Follow-up
Assessment Number	Assessment 1	Assessment 2	Assessment 3	Assessment 4	Assessment 5
Scheduled Day	One the day before surgery	Day 1, time 1	Day 1, time 2: 15 minutes after surgery	Day 1, time 3: 40 minutes after surgery	3 days after surgery
Scheduling Window		>90 minutes	±5 minutes	±5 minutes	±1 days
Informed Consent	X				
PQRS test	X		X	X	X
Medical History	X				
Entry Criteria	X	X			
(Serious)Adverse Events	X	X	X	X	X
Physical Examination	X				
Patient Data online recording		X			
Patient randomization		X			
Patient Satisfaction evaluation					X
Dispense Trial Medication		X			
Pregnancy test	x				

Can adequacy of anesthesia depth and quality of recovery be influenced by the level of neuromuscular blockade?

f) Randomization and blinding procedures

This will be an interventional, randomized and unblinded study, performed at a single center (Centro Hospitalar do Porto).

Patient randomization will be done by a computer software programmed with a varying block randomization technique (to ensure sample size due to the small number of patients in each group), using a uniform distribution. The software will be installed in the data collection computer, and the anesthesiologist will only know to which group the patient was randomly assigned before induction starts. Although block randomization is used, the computer software does not display information about the block assignment of future patients to the user. The software is programmed using the Statistical toolbox of MATLAB.

g) Treatment

Trial participants will be randomly assigned (using varying block randomization) to one of two groups:

- Group 1 – Standard Clinical Practice Group - standard NMB, with a standard rocuronium dose for intubation (0.6 mg/kg). If required, the reversal of neuromuscular block is performed with neostigmine.
- Group 2 – Deep NMB group - with a standard rocuronium dose for intubation (0.6 mg/kg), followed by a constant infusion of rocuronium (10-15 µg/kg/min) to guarantee a PTC less or equal to 2 on the TOF monitor (PTC is evaluated every 5 minutes). The reversal of neuromuscular block is performed with Sugammadex (4 mg/kg).

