General anesthesia will be performed with total intravenous technique using the hypnotic propofol, the analgesic remifentanil and the neuromuscular relaxant rocuronium. Target controlled infusion (TCI) will be used for propofol and remifentanil. Standard routine anesthesia practice for these procedures uses total intravenous anesthesia with propofol and remifentanil by TCI and rocuronium. A single bolus dose of rocuronium is given for tracheal intubation

Can adequacy of anesthesia depth and quality of recovery be influenced by the level of neuromuscular blockade?

and no further doses are administered during the procedure. At the end of surgery, NMB is reversed only if TOF is below 90%

h) Treatment duration

Study treatment will be administered during surgery only, on day one.

i) Discontinuation criteria

A patient may request to discontinue from the clinical trial at any time for any reason.

The investigator in any case in which emerging effects are of unacceptable risk to the individual subject, will discontinue the patient from the study. In addition, the investigator will stop study for any patient with unmanageable factors that may interfere significantly with the trial procedures and/or the interpretation of results.

If the MAP does not respond to the protocol steps described in section 8, then the study should be stopped for that subject.

j) Investigational product accountability

These requirements apply only to Sugammadex, which is already commercialized in Portugal and is used in current clinical practice at the Centro Hospitalar do Porto.

The internal labeling will be performed by our pharmacy department according to GCP guidelines and the local regulations for clinical trials. All drugs used, except for Sugammadex, will be labelled according to standard practice.

Can adequacy of anesthesia depth and quality of recovery be influenced by the level of neuromuscular blockade?

The investigator will be responsible for the destruction of the supplies of Sugammadex at the study center pursuant to the GCP Guidelines, local regulations and the investigator's institutional policies.

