5. Patients that are able to and do provide a signed informed consent form

b) Exclusion criteria

1. Patients with neuromuscular diseases and severe cardiac and respiratory pathologies
2. Contra indication for any of the drugs used
3. Not able to complete the baseline PQRS test.
4. Indication to perform tracheal intubation using fibroscopy
5. Patients who are pregnant or nursing

c) Discontinuation criteria

A patient may request to discontinue from the clinical trial at any time for any reason.

The investigator in any case in which emerging effects are of unacceptable risk to the individual subject, will discontinue the patient from the study. In addition, the investigators will stop study for any patient with unmanageable factors that may interfere significantly with the trial procedures and/or the interpretation of results.

Can adequacy of anesthesia depth and quality of recovery be influenced by the level of neuromuscular blockade?

If the MAP does not respond to the protocol steps listed in section 8, then the study should be stopped.

Can adequacy of anesthesia depth and quality of recovery be influenced by the level of neuromuscular blockade?

8. Treatment of study participants

a) Informed Consent

Informed consent will be obtained by a medical investigator, part of the study team, during Assessment 1.

b) Study procedures

Minimum duration of surgery is 90 minutes and general anesthesia will be performed with total intravenous technique using the hypnotic propofol, the analgesic remifentanyl and the neuromuscular relaxant rocuronium. Target controlled infusion (TCI) will be used for propofol and remifentanyl. Standard routine anesthesia practice for these procedures uses total intravenous anesthesia with propofol and remifentanyl by TCI and rocuronium. A single bolus dose of rocuronium is given for tracheal intubation and no further doses are administered during the procedure. At the end of surgery, NMB is reversed only if TOF is below 90%.

i. Assessment 1

Assessment name: Pre-anesthesia

Timing: One the day before surgery

Informed Consent
PQRS test
Medical History
Pregnancy test
Entry Criteria
(Serious) Adverse Events
Physical Examination

Can adequacy of anesthesia depth and quality of recovery be influenced by the level of neuromuscular blockade?

Patient Data online recording
Patient randomization

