- If no EMG activity is present, the propofol effect-site target concentration is increased by steps of 0,5 µg/ml until the concentration required for loss of consciousness is achieved.

Response Protocol to Mean Arterial Pressure (MAP) values outside the target interval:

- If MAP is more than 30% below the baseline value, an ephedrine bolus of 5 mg is given every 3 minutes until the desired effect;
- If MAP is more than 30% above the baseline value, the remifentanil effect-site target concentration is increased by steps of 1,5 ng/ml until a maximum of 15 ng/ml is achieved. If the MAP value does not decrease to the desired range, then the propofol effect-site target concentration is increased by steps of 0,5 µg/ml until the value required for loss of consciousness is achieved;
- If the MAP still is outside the desired interval, then a 10 mg dose of Labetalol should be administer every 10 minutes until the desired effect.

If the MAP does not respond to the previous protocol steps, then the study should be stopped.

Additional rocuronium (muscle relaxant) bolus of 0.2 mg/kg are allowed in the following situations:

Can adequacy of anesthesia depth and quality of recovery be influenced by the level of neuromuscular blockade?

- If during surgery, the surgeon mentions difficulties due to muscle contraction
- If the patient is showing spontaneous ventilation that prevents adaptation to mechanical ventilation

i. Assessment 3

Assessment name: 15 minutes PQRS Test

Timing: Day 1, time 2: 15 minutes after surgery

PQRS test
(Serious) Adverse Events

After the patient is moved from the surgery room to the recovery room, the PQRS test is performed in both groups at 15 minutes post-surgery. The PQRS tests are recorded in the patient's individual CRF forms.

ii. Assessment 4

Assessment name: 40 minutes PQRS test

Timing: Day 1, time 3: 40 minutes after surgery

PQRS test
(Serious) Adverse Events

The PQRS test is performed in both groups of patients at 40 minutes post-surgery.

Can adequacy of anesthesia depth and quality of recovery be influenced by the level of neuromuscular blockade?

The main study finishes after the 40 minutes PQRS test is performed.

iii. Assessment 5

Assessment name: Follow-up

Timing: 3 days after surgery

(Serious) Adverse Events
Patient Satisfaction evaluation

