Sample size calculation with a power of 0.80 and an α of 0.05, considering the primary hypothesis of a reduction in the BIS variability (measured as the standard deviation) and a reduction in the propofol and remifentanil drug consumption (measured as the average effect-site concentration required) during maintenance of anesthesia.

To estimate the standard deviation of our population, we searched our database for standard clinical practice cases with: online data recording; cervical spine surgery; BIS average values within the recommended target values [40-60]; TCI anesthesia with propofol and remifentanil.

A total of 12 patients data were analyzed (mainly due to the lack of online recording during the procedures), the average BIS standard deviation was 8.7 ± 3.14 , and the average propofol and remifentanil effect-site concentrations were 2.68 ± 0.9 $\mu\text{g/ml}$ and 2.83 ± 0.8 ng/ml , respectively.

Can adequacy of anesthesia depth and quality of recovery be influenced by the level of neuromuscular blockade?

A 25% reduction on the BIS variability (standard deviation) was considered clinically relevant, and gave a minimum sample size of 26 per group.

A reduction on propofol average effect-site concentration of 20% was considered clinically relevant, and gave a minimum sample size of 34 per group.

A reduction on remifentanil average effect-site concentration of 20% was considered clinically relevant, and gave a minimum sample size of 24 per group.

Considering the above results and the possibility of patient exclusion due to external complications during surgery, a total of 35 patients per group will be included in the study.

The secondary variable, result of the PQRS test was not used in the sample size calculation, since there are no studies on the comparison of recovery after two different interventions and the data regarding sample calculation that the authors of PQRS showed us are for the recovery at 3 days post-surgery, which is not comparable to our study. Therefore we did not consider adequate to estimate a percentage difference for which we do not know the clinical reality.

The surrogate variables, consumption of ephedrine and labetalol will be analyzed since these drugs are used in the response protocol to target deviations, but they are not considered for the sample size calculation.

c) Level of statistical significance

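### Open-label stops after randomisation, including one to protect interpretation, leave the intention-to-treat analysis not assured for stopped patients

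*Combined protocol and SAP*

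**What the plan says.** Section 6f: "This will be an interventional, randomized and unblinded study". The anesthesiologist learns the allocation before induction, so every stop during surgery is made with the arm known.

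Section 6i gives three grounds for a stop besides the patient's own request:

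- unacceptable risk to the patient;
- a discretionary ground: "the investigator will stop study for any patient with unmanageable factors that may interfere significantly with the trial procedures and/or the interpretation of results";
- a blood-pressure ground: "If the MAP does not respond to the protocol steps described in section 8, then the study should be stopped for that subject".

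Section 7c repeats them ("the investigators will stop study for any patient with unmanageable factors").

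For MAP more than 30% above baseline, section 8 sets the order of response. First, "the remifentanil effect-site target concentration is increased by steps of 1,5 ng/ml until a maximum of 15 ng/ml is achieved". Next, propofol is raised in steps up to the level recorded at loss of consciousness. Last, "a 10 mg dose of Labetalol should be administer every 10 minutes until the desired effect". Section 6a makes the effect-site concentrations of both drugs primary endpoints, beside BIS variability.

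On what follows a stop:

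- Section 10 treats participation as over once a patient discontinues prematurely.
- The Discontinuation Visit in section 8 lists adverse events and satisfaction only.
- Section 11b plans for "the possibility of patient exclusion due to external complications during surgery, a total of 35 patients per group will be included in the study".
- Section 11e leaves out participants whose primary endpoint data are missing.
- Section 11g says that all data are included and calls this intention to treat.

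**The concern.** A stop to protect interpretation is not a safety stop, which the preceding sentence of 6i already covers. It comes after randomisation, is a matter of judgement with the arm known, and has no list of factors and no threshold. The high-MAP stop comes only after remifentanil, and then propofol, have been raised under the protocol. A patient who leaves by that route therefore tends to have high values on two primary endpoints.

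No sentence says whether a maintenance record cut short by a stop is a valid endpoint or a missing one, and no minimum length is set. That choice could be made after the results are seen. If stopped patients are dropped, the comparison is no longer between the groups as randomised. Since section 10 ends participation, the 15- and 40-minute PQRS, which are secondary endpoints, may be lost for the same patients.

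**Working it through.** **The rules side by side**

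- 11g, read literally, keeps whatever was recorded. Data are logged every 5 seconds (section 9b), so a record up to the stop will normally exist.
- 11e drops a patient only if primary data are missing, but does not say whether a truncated record counts as missing.
- 11b foresees exclusion because of events during surgery, hence after randomisation, and does not define it.
- Sections 8 and 10 end participation without requiring recording or PQRS to continue.

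11e and 11g can be read together as an available-case analysis. Nothing in the text settles that a stopped patient is in it.

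**The plan's own sample size**

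For propofol, the difference is 0.20 × 2.68 = 0.536 with SD 0.9. The formula is n = 2(z_α + z_β)² SD²/difference², with power 0.80.

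- One-sided α of 0.05: 2 × (1.645 + 0.842)² × 0.81/0.2873 = 34.9, so 35, close to the stated figure ("gave a minimum sample size of 34 per group").
- Two-sided α of 0.05: 44.3, so 45.

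The stated figures fit a one-sided test. That is a separate matter. On the plan's own figures the margin over the minimum is 35 − 34 = 1 per arm for propofol, 35 − 26 = 9 for BIS variability and 35 − 24 = 11 for remifentanil.

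**Illustration: one high-MAP stop deleted from one arm**

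From the documents: remifentanil mean 2.83 and SD 0.8 ng/ml, ceiling 15 ng/ml, labetalol interval 10 minutes, 35 per arm, target difference 0.20 × 2.83 = 0.566.

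Assumed: k = 1 to 3 labetalol intervals at the ceiling; a record of L = 60 to 120 minutes up to the stop; 2.83 ng/ml for the rest of it; ramp time ignored; the other 34 patients averaging 2.83; the whole patient deleted.

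- Fraction of the record at the ceiling: f = 10k/L, from 10/120 = 0.083 to 30/60 = 0.50.
- Patient's excess over the mean: d = f × (15 − 2.83) = f × 12.17.
- Fall in the arm mean on deletion: d/35.

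| L (min) | k = 1 | k = 2 | k = 3 |
|---|---|---|---|
| 120 | 0.029 (5%) | 0.058 (10%) | 0.087 (15%) |
| 90 | 0.039 (7%) | 0.077 (14%) | 0.116 (20%) |
| 60 | 0.058 (10%) | 0.116 (20%) | 0.174 (31%) |

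Entries are in ng/ml, with the share of 0.566 in brackets.

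For propofol, assume a loss-of-consciousness concentration C of 4 to 6 µg/ml, which the documents do not give. The shift is f × (C − 2.68)/35. It runs from 0.083 × 1.32/35 = 0.003 µg/ml (0.6% of 0.536) to 0.50 × 3.32/35 = 0.047 µg/ml (9%).

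No figure is offered for BIS variability, because the MAP route has no BIS trigger. None is offered for the discretionary stop, because nothing in the documents bears on its frequency.

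**Sign**

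Deletion from Group 2 would exaggerate the drug saving with deep block; deletion from Group 1 would hide it. Balanced stops would roughly cancel.

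**The case against.** The strongest reply is that 11g already answers the question: all data are included, so a partial record stays, and 11e removes only patients with nothing to analyse. The exclusions foreseen in 11b may be no more than an allowance for those losses. Section 8 also says the 15- and 40-minute PQRS are done in both groups, and nowhere says that the Discontinuation Visit replaces them. This stands in part. A reader might infer that the plan discards stopped patients, or that their PQRS is certain to be lost. The documents support only that neither is settled.

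A reader might also infer that the investigator may stop anyone whose result is unwelcome. The criterion is narrower: the factors must be unmanageable and the interference significant.

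The 31% is not an estimate of bias. It needs whole-patient deletion, against the literal sense of 11g, in one arm only, with 30 of 60 minutes at the ceiling. It describes the high-MAP stop, which has a numerical trigger, and not the discretionary one. A low-MAP stop follows ephedrine and involves no prescribed rise in either drug.

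Nor does the margin of one patient show a serious loss of power. It belongs to propofol, where the illustrated shift is small, and a fall from 35 to 33 per arm takes two-sided propofol power only from 0.69 to 0.66. The margins for remifentanil and BIS are 11 and 9.

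**Conclusion.** The concern holds in a limited form. The rules permit loss after randomisation that is decided with the arm known and, on the high-MAP route, is related to two primary endpoints. They end participation in a way that can cost the early PQRS. The intention-to-treat statement in 11g does not by itself secure these patients' place in the analysis.

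The size and direction of any bias are unknown. It is about zero if stops are balanced between arms or if the recorded data are used. The illustration shows only that a single deleted patient could matter for remifentanil and would matter much less for propofol. It depends on the assumed time at the ceiling, record length and deletion. The change is a cheap improvement that should be made. Confidence is medium, because no stop rate is given and 11g can be read favourably.

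**What to change.** 1. In 6i and 7c, delete interference with interpreting the results as a ground for stopping.
2. In 6i, 7c, 8 and 10, state that a stop ends only the study's titration and block rules. Unless consent is withdrawn, online recording continues to the end of surgery, and the 15- and 40-minute PQRS and the day-3 contact are done.
3. In 11b and 11e, state that a stopped patient stays in the randomised group and is analysed with all recorded maintenance data, with data up to the stop as a sensitivity analysis. Primary data are missing only if there is no usable maintenance record, and exclusion in 11b means only that. Fix in advance what is usable, for example 30 minutes (30 × 60/5 = 360 samples); the value is for the sponsor to choose.
4. Report stops by arm, with time and reason, including those on the remaining trial-procedures ground.

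All recorded data should be the main analysis because a record cut at the stop gives extra weight to the escalation. With 30 minutes at the ceiling, the patient moves the arm mean by 0.174 ng/ml on a 60-minute record up to the stop. On a 120-minute full record, assuming a return to 2.83 afterwards, the figure is 0.087.

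No new equipment or visits are needed. A protocol amendment is, and 11f sends statistical changes to the authorities beforehand. Some records will be short or extreme, and time after the stop reflects care outside the study rules.

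Precision also falls. With the patient kept, the arm SD is √[(33 × 0.8² + (34/35)d²)/34], which rises from 0.80 to between 0.81 (f = 0.083) and 1.30 (f = 0.50). The standard error of the difference, √[(0.8² + SD²)/35], rises from 0.191 to between 0.192 and 0.257, that is by under 1% to 35%. With f = 0.25, as on the 120-minute full record above, the SD is 0.94 and the standard error 0.209, a rise of 9%.

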We hypothesise that an anesthetic protocol maintaining deep neuromuscular block throughout the entire surgical procedure followed by sugammadex reversal, would suppress EMG activity and result in improved anesthetic stability by reducing the variability of the Bispectral Index of the EEG, and be beneficial by reducing the total doses of the anesthetic drugs propofol and remifentanyl required to maintain an adequate level of anesthesia (BIS between 40 and 60). Average anesthetic requirements will be assessed by using the average effect-site concentrations of propofol and remifentanyl, since they take into account the patient gender, weight and height and are, therefore, more representative of the drug requirements.

As secondary hypothesis we also expect to observe an increase in the quality of recovery (assessed by the Postoperative Quality of Recovery Scale – PQRS) and a decrease in the amount of ephedrine and labetalol used during the surgical procedure (drugs used in response to haemodynamic instability), when deep neuromuscular block is used.

a) Investigational Medicinal Product

The goal of the current study is to obtain additional data on two different anesthetic approaches, which includes drugs used according to their approved use and doses. By design, we will only obtain additional information on Sugammadex, with systematic collection and evaluation of adverse events for this drug. As such, the Investigational Product in this study is sugammadex.

The use of neostigmine in Group 1 fulfills criteria of a rescue medication. The remaining drugs are considered background medication, used according to approved and standard practice and no additional information will be collected concerning these drugs.

Can adequacy of anesthesia depth and quality of recovery be influenced by the level of neuromuscular blockade?

All drugs, including sugammadex, will be used according to their approved and standard use at the trial site. Information concerning Sugammadex is contained in the attached Summary of Product Characteristics.

Sugammadex used for the trial will be supplied by MSD and will be relabeled and accounted for according to requirements for Investigational Medicinal Products.

The remaining drugs used during the trial will be supplied locally by CHP, according to standard procedures.

b) Risks and benefits

The risks and benefits of Sugammadex are those described by the Summary of Product Characteristics:

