The primary hypothesis is that there is a better anesthetic stability in the deep NMB group (Group 2) and that this is translated as a reduction of the BIS signal variability and a reduction in the required effect-site concentrations of propofol and remifentanyl (representative of the total drug consumption).

b) Secondary objectives

As a secondary objective, we will study the quality of recovery using the PQRS scale to see if maintaining a deep NMB level during surgery has an impact on the patients' quality of recovery.

The secondary hypothesis is that the quality of recovery (PQRS test) is better in the patients of Group 2.

Can adequacy of anesthesia depth and quality of recovery be influenced by the level of neuromuscular blockade?

6. Study design

Patients subjected to anterior cervical spine surgery under general intravenous anesthesia will be randomized to receive one of two protocols regarding the neuromuscular blockade:

- Group 1 – Standard Clinical Practice Group - standard NMB, with a standard rocuronium dose for intubation (0.6 mg/kg). If required, the reversal of neuromuscular block is performed with neostigmine.
- Group 2 – Deep NMB group - with a standard rocuronium dose for intubation (0.6 mg/kg), followed by a constant infusion of rocuronium (10-15 µg/kg/min) to guarantee a PTC less or equal to 2 on the TOF monitor (PTC is evaluated every 5 minutes). The reversal of neuromuscular block is performed with Sugammadex (4 mg/kg).

a) Primary Endpoints

- BIS signal variability using the measured standard deviation during the maintenance phase of anesthesia
- Required effect-site concentrations of remifentanyl and propofol

b) Secondary Endpoints

- PQRS results at 15 and 40 minutes after surgery (taking into account the patient baseline values of the PQRS test done on the pre-anesthetic visit)
- PQRS results at day 3 after surgery

c) Study type

This is an interventional, phase 4, double-arm, parallel, randomized, open-label, single-center study aiming to compare two anesthesia protocols.

Can adequacy of anesthesia depth and quality of recovery be influenced by the level of neuromuscular blockade?

d) Study Timeline

- Study Start Date: April 2016
- Study End Date: April 2017
- First Patient In: April 2016
- Last Patient In: April 2017
- Last Patient Out: April 2017
- Study Analysis: May 2017
- Publication: November 2017

Can adequacy of anesthesia depth and quality of recovery be influenced by the level of neuromuscular blockade?

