Clinical supplies of the drug Sugammadex will be received by a designated person of the pharmacy department at the site, handled and stored safely and properly, and kept in a secured location. Clinical supplies are dispensed in accordance with the protocol, i.e. the pharmacy will be informed of the patient randomization and the need for the use of Sugammadex in the beginning of the surgery and the drug will be sent to the operating room.

The investigator will keep accurate records of the clinical supplies and the amount dispensed for each patient assigned to Group 2.

k) Blinding and Un-blinding procedures

Not applicable.

l) Source documents and data collection

Part of data will be recorded electronically: Trial participants will be monitored with standard ASA monitoring. Additional monitoring (i.e. intra-arterial pressure) will be provided depending on patient clinical status. The monitoring equipment is as follows:

- TOF Watch SX monitor for neuromuscular block assessment
- BIS – Bispectral Index Monitor (Covidien)
- Aisys Anaesthesia Monitor (General Electrics - GE)
- Fresenius Orchestra Base Primea, with TCI for propofol and remifentanyl
- Syringe pump attached to the Fresenius Base Primea for the continuous infusion of rocuronium

Data collection software (Rugloop® Software and TOF Link) is installed on a Laptop computer connected to the Base Primea infusion pumps, the BIS monitor,

Can adequacy of anesthesia depth and quality of recovery be influenced by the level of neuromuscular blockade?

GE monitor and TOF Watch monitor, allowing for all data to be recorded online. The patient data files generated by the Rugloop® software will be accessed using the Labgrab® software and exported to excel files. TOF watch data will also be exported to excel files. All online data is posteriorly recorded in a patient individual CD.

All non-electronic data will be noted on the patients' paper CRF and on the RugLoop® software notes toolbar.

Can adequacy of anesthesia depth and quality of recovery be influenced by the level of neuromuscular blockade?

7. Selection and discontinuation criteria

a) Inclusion criteria

1. Patients ASA I-III
2. Between 18 – 80 years old
3. Scheduled for routine cervical surgery
4. Minimum duration of surgery is 90 minutes and performed with total intravenous anaesthesia (TIVA) with the hypnotic propofol, the analgesic remifentanyl and the neuromuscular relaxant rocuronium

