Data collection software (Rugloop® Software and TOF Link) are installed on a Laptop computer connected to the Base Primea infusion pumps, the BIS monitor, GE monitor and TOF Watch monitor, allowing for all data to be recorded online. The patient data files generated by the Rugloop® software will be accessed using the Labgrab® software and exported to excel files. TOF watch data will also be exported to excel files. All online data is posteriorly recorded in a patient individual CD. All non-electronic data will be noted on the patients' paper CRF and on the RugLoop® software notes toolbar.

The total doses of ephedrine and labetalol are used as a surrogate variable, since they are the drugs used in the response protocol to hemodynamic instability (MAP being outside the desired target range).

The following recorded data will be analyzed per patient and compared between the two study groups:

- BIS signal variability using the measured Standard deviation during the maintenance phase of anesthesia
- BIS average value during the maintenance phase of anesthesia
- Duration of periods of BIS values above 60 and below 40
- Average effect-site concentrations of propofol and remifentanil required during the maintenance of anesthesia
- Total doses of remifentanil, propofol, ephedrine and labetalol

Can adequacy of anesthesia depth and quality of recovery be influenced by the level of neuromuscular blockade?

- PQRS results at 15 and 40 minutes after surgery (taking into account the patient baseline values of the PQRS test done on the pre-anesthetic visit)
- Patient satisfaction evaluated using the specific PQRS questions

Can adequacy of anesthesia depth and quality of recovery be influenced by the level of neuromuscular blockade?

10. Safety evaluation

Each patient is considered to have ended participation in the study when he/she has completed the last telephone contact at 3 days post-surgery to verify the occurrence of any adverse events (AE) according to the pharmacovigilance guidelines, or prematurely discontinues from the trial.

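### Drug totals and time outside the BIS range are compared unscaled, which costs precision in supporting outcomes because length of surgery has no upper limit

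*Combined protocol and SAP*

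**What the plan says.** Section 9 b) introduces its list with "The following recorded data will be analyzed per patient and compared between the two study groups". Two of the items are "Total doses of remifentanil, propofol, ephedrine and labetalol" and "Duration of periods of BIS values above 60 and below 40". Neither is expressed per kg, per hour or as a share of recorded time. The items on BIS SD, mean BIS and effect-site concentration in the same list are limited to the maintenance phase; these two are not.

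On length of surgery, section 7 a) says only "Minimum duration of surgery is 90 minutes". No maximum, mean or SD appears anywhere.

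Section 11 a) analyses continuous data with an independent-samples t test, or repeated-measures ANOVA where measurements repeat. ANCOVA appears only in the sentence on PQRS and names no covariate. Group comparability is checked for age, weight and height, not for duration.

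Section 4 hypothesises a benefit from "reducing the total doses of the anesthetic drugs propofol and remifentanyl required to maintain an adequate level of anesthesia" and, as a secondary hypothesis, less ephedrine and labetalol. Section 9 b) treats those two totals as a surrogate for haemodynamic instability. Section 4 also explains that average effect-site concentrations were chosen to measure requirement "since they take into account the patient gender, weight and height and are, therefore, more representative of the drug requirements". Section 6 a) accordingly makes "Required effect-site concentrations of remifentanyl and propofol" a primary endpoint beside BIS SD.

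**The concern.** A total dose is a rate of use multiplied by the time over which the drug runs. For weight-scaled drugs it is also multiplied by weight. Minutes outside a BIS range are a fraction of time multiplied by recorded time. If operations vary in length, two patients with the same requirement and the same stability will have different values. That variation says nothing about depth of block, but it enters the standard error of the unadjusted comparison.

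The problem matters most where no scaled version is planned. Propofol and remifentanil already have average effect-site concentrations. BIS excursion time, ephedrine and labetalol have no such counterpart. Section 8 b) allows ephedrine to be repeated every 3 minutes and labetalol every 10, so a longer anesthetic gives more opportunities to dose at equal stability.

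At stake are a weaker test of a stated secondary hypothesis and of the total-dose hypothesis, and an ambiguous reading if operating time differs between arms.

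**Working it through.** **The plan's own figures.** Section 11 b) gives no sample size or power for totals or excursion time. Its sample sizes concern BIS SD (8.7 ± 3.14, 25% reduction), propofol concentration (2.68 ± 0.9, 20%) and remifentanil concentration (2.83 ± 0.8, 20%). With n = 2(z_α + z_β)² SD²/δ² and power 0.80:

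| Outcome | δ/SD | n, one-sided 0.05 | n, two-sided 0.05 | Stated n |
|---|---|---|---|---|
| BIS SD | 2.175/3.14 = 0.693 | 26 | 33 | 26 |
| Propofol | 0.536/0.9 = 0.596 | 35 | 45 | 34 |
| Remifentanil | 0.566/0.8 = 0.708 | 25 | 32 | 24 |

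The stated values are reproduced, to within one patient, by a one-sided test. The calculations below use two-sided 0.05.

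**Inputs for totals.**
- From section 11 b): CV of rate, propofol 0.9/2.68 = 0.336 and remifentanil 0.8/2.83 = 0.283; 35 per group; 20% reduction.
- Assumed, because the documents give no figure: weight CV 20%; duration CV 20%, 30% and 40%; rate, weight and duration independent and log-normal. The pilot CVs are for effect-site concentrations and are borrowed for per-kg-per-hour rates.

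**Spread of a total.** With total = rate × weight × duration,

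CV_total = √[(1 + CV_rate²)(1 + CV_weight²)(1 + CV_duration²) − 1].

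Propofol at duration CV 30%: √(1.113 × 1.04 × 1.09 − 1) = 0.51. Remifentanil: √(1.080 × 1.04 × 1.09 − 1) = 0.47.

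**Power, by simulation (20,000 trials per scenario, t test).**

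| | Scaled rate | Raw total, duration CV 20% | 30% | 40% |
|---|---|---|---|---|
| Propofol | 78% | 54% | 44% | 35% |
| Remifentanil | 90% | 61% | 50% | 40% |

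An equal-SD normal formula gives lower levels and a similar loss: 70% to 37% for propofol and 84% to 42% for remifentanil at duration CV 30%. Over weight CV 10–25% and duration CV 20–50%, that formula puts raw-total power at 23–53% for propofol and 25–63% for remifentanil.

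**Outcomes with no scaled counterpart.** The documents give no SD for BIS excursion time, ephedrine or labetalol, so their power cannot be computed. If such an outcome is proportional to duration and its per-hour CV is c, scaling removes CV_duration²(1 + c²) from the relative variance. Relative to c², the raw measure therefore needs a sample larger by CV_duration²(1 + 1/c²). This is always more than CV_duration², that is, more than 4%, 9% and 16% at duration CVs of 20%, 30% and 40%. The cost is greatest when the outcome itself varies little between patients.

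**False positives.** The 95% range for a chance difference in mean duration is ±1.96 × CV × √(2/35), or ±9%, ±14% and ±19% at the three CVs. The t test already allows for this. With no true effect and the same duration distribution in both arms, raw propofol totals reject in about 4.9% of trials (duration CV 30%, 40,000 runs).

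If duration is truly 5%, 10% or 20% shorter in one arm and the requirement rate is identical, raw totals reject in 7%, 14% and 44% of trials. The scaled rate stays at 5%.

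**The case against.** The strongest reply is that the plan already handles this where it matters most. The primary drug endpoint is an average effect-site concentration, which takes account of body size and does not accumulate with time, and the trial is sized on it. Section 6 lists neither totals nor excursion time as a primary or secondary endpoint. That stands. It also means that the power figures above fall on the two drugs that least need the change.

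A second reply is that totals answer a question the plan asks. Section 4 hypothesises lower total doses and mentions cost. If deep block shortened surgery, a per-hour rate would hide a real saving. That also stands, and it is a reason to keep the totals as a stated comparison.

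Two stronger readings are tempting, and the documents support neither. A reader might infer that weight distorts every listed item. It does not: minutes outside a BIS range do not scale with weight, and section 8 b) gives ephedrine and labetalol as fixed boluses of 5 mg and 10 mg. A reader might also infer that chance imbalance in operating time will create spurious treatment effects. Randomisation and the t test keep that error near 5%. A systematic false signal of lower requirement needs duration to differ by arm. That is possible, because duration arises after randomisation, the trial is open-label and section 4 expects better surgical conditions under deep block. Nothing in the documents shows that it will happen.

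**Conclusion.** The point holds as a loss of precision in supporting outcomes, with a conditional risk of misreading. The primary endpoints are untouched, and the plan claims no power for totals. BIS excursion time and the ephedrine and labetalol totals are the outcomes most in need of scaling, because they grow with length of anesthesia and have no scaled version. The loss can be quantified only for propofol and remifentanil totals, where raw comparison takes power from about 78% to 54–35% and from about 90% to 61–40%. These values depend on the assumed weight and duration CVs and on the borrowed pilot CVs. The direction does not: power fell in every scenario tried. The change is worth making before analysis, because it also settles the scale in advance.

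**What to change.** In section 9 b), name these as the measures of stability and requirement:
- BIS above 60 and BIS below 40, each as a percentage of recorded maintenance time, with the start and end of maintenance defined;
- ephedrine and labetalol per hour of anesthesia;
- propofol and remifentanil per kg per hour.

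Keep the raw totals as an additional comparison, since they address the total-dose hypothesis and cost. Report duration of anesthesia by group, so that a difference in totals can be separated into rate and time.

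The cost is wording only. Weight is already analysed, and the BIS and pump data are recorded every 5 seconds. The downside is a few more supporting comparisons. A per-hour rate will also not show a dose saving that comes from shorter surgery, which is why the totals stay.
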